the study. Explain if the research involves the review of records (including public databases or registries) with identifiable private information. If so, describe the type of information gathered from the records and if identifiers will be collected and retained with the data after it is retrieved. Describe the kinds of identifiers to be obtained, (i.e. names, social security numbers) and how long the identifiers will be retained and justification for use and/or evaluations.

We are planning to recruit and enroll up to 30 participants through recruitment material that will be sent out through email and posted on fliers (see recruitment material attached). Inclusion criteria will be: (a) age 21-39 years old, (b) less than 4 drinking days and less than 12 drinks per week on average in the past 2 months, (c) have consumed at least 4(women) or 5 (men) drinks on one occasion, in the past year without experiencing adverse effects (c) a valid photo ID (d) willing and able to use a rideshare credit or septa token as transportation home from the study visit. Exclusion criteria will be (a) desire alcohol treatment now or received it in the past 6 months, (b) alcohol use disorder with withdrawal per DSM-V criteria and (c) non-English-speaking, and (d) women who are pregnant (e) individuals who should not consume alcohol due to a medical condition. Individuals, who are interested in the study, will be contacted and screened over the telephone using our Alcohol Study Screener (attached to this protocol). All participants who meet inclusion criteria will be invited to consent to the study.

Interested participants will call the study hotline where an IRB-approved research assistant or project manager, will answer any questions, administer the study screening and go over the written informed consent. There will be an optional in person study visit for the participant to come in and review study procedures, and sign written informed consent, in person. At the study visit, which occurs at a predetermined time, the participant will first sign written informed consent to participate. They will then take an initial survey, with questions related to their past alcohol use and habits including Driving History and Experience Questionnaire DHEQ1, Drinking and Driving Questionnaire. Participants will also take the Decision making survey, which includes The Barratt Impulsiveness Scale, and the Delayed discounting questionnaire.

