Some participants will wear the BACtrack Skyn wrist device, which will start collecting alcohol measurements after the first dose of alcohol. Participants will then receive three doses of vodka mixed with juice based on their gender and weight designed to reach a peak blood alcohol level of .10 g/dL. After each dose, their Breath Alcohol Content (BrAC) will be measured using the BacTrack Mobile device. After each breathalyzer measurement, participants will receive the Self-Report of Intoxication Survey, which will include Perceived Driver Fitness and Perceived intoxication and BAC estimation, which are measured using a visual analogue scale.

For the control group, participants will remain blinded to the BrAC readings on the BacTrack mobile app. For the intervention group, the participants will be shown their BrAC readings on the BacTrack mobile app before completing their Self-Report of Intoxication Survey.

Besides a preliminary study visit for participants to consent to the study and complete the eligibility survey, all research activities will take place in one of the four CTRC study sites and will occur in a study session of approximately six hours in length with up to four participants at each session. Participants will be separated into different research rooms at the CTRC.

Data collection will include contact information, medical history, and history of alcohol use, various measurements of Breath Alcohol Content (BrAC), as well as survey data from the self-reported

intoxication survey. The informed consent process during study enrollment will describe all of these aspects of data collection.

Attached to this protocol are the following study instruments for data collection and recruitment:

1. Written Informed Consent
2. Screening Survey
3. Eligibility Survey
4. Intake Survey
5. Decision making survey
6. Self-Reported intoxication Survey

Describe how and who manages confidential data, including how and where it will be stored and analyzed. For instance, describe if paper or electronic report forms will be used, how corrections to the report form will be made, how data will be entered into any database, and the person(s) responsible for creating and maintaining the research database. Describe the use of pseudonyms, code numbers and how listing of such identifiers will be kept separate from the research data.

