#### Key Exclusion Criteria

Exclusion criteria will be: (a) a desire for alcohol treatment now or received it in the past 6 months, (b) alcohol use disorder per DSM-V criteria and (c) substance use disorder within the past 12 months per DSM-V criteria (d) a prior psychiatric condition requiring hospitalization (e) non-English-speaking (f) individuals who have a medical condition or who are taking medication which limits or prevents the consumption of alcohol (g) suicidal ideation. We are excluding non-English speaking individuals due to the fact that we do not have translated materials so they will be unable to consent to participate in the study activities. We are also excluding individuals who are under 21 years in age due to legal restrictions of consuming alcohol. We are excluding individuals who have psychological or medical conditions, or are taking medication, that limit or prevent the consumption of alcohol.

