1. Recruitment: We will use broad-based and cost-effective recruitment strategies including: a) advertisements in UPHS and CHOP employee weekly emails; and b) posting of flyers. Individuals, who are interested in the study, will be contacted and screened over the telephone.
2. Phone Screening: General information will be provided to the prospective subject. Study screening form (attached) will be administered, eligibility confirmed, and research staff will go over informed consent with participant. Participants will have the option to have the informed consent form emailed to them prior to the study visit. Columbia suicide severity rating scale will be administered. Inclusion criteria will be: (a) age 21-39 old, (b) Less than 4 drinking days and 12 drinks per week on average in the past 2 months, (c) have consumed either 4 (women) or 5 (men) or more standard drinks on a single occasion without problems (d) a valid photo ID (e) willing to take public transportation home, via septa or a rideshare credit. Exclusion criteria will be (a) desire alcohol treatment now or received it in the past 6 months, (b) alcohol dependence with withdrawal per DSM-V criteria (c) non-English-speaking, and (d) individuals who have a medical condition or who are taking medication which limits or prevents the consumption of alcohol. Interested and eligible participants will schedule their study visit.

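### Phone screening and the survey-administration section exclude alcohol use disorder only where there is withdrawal; the Key Exclusion Criteria exclude it without that condition

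*Combined protocol and SAP*

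**What the plan says.** The combined protocol describes eligibility in several places.

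- **Procedures, item 2 (Phone Screening).** The alcohol-disorder exclusion reads "b) alcohol dependence with withdrawal per DSM-V criteria (c) non-English-speaking". The same item gives the step its function: "Study screening form (attached) will be administered, eligibility confirmed". Those found eligible then book the study visit.
- **Administration of Surveys and/or Process.** A second full list gives "b) alcohol use disorder with withdrawal per DSM-V criteria".
- **Key Exclusion Criteria.** The exclusion here is "b) alcohol use disorder per DSM-V criteria and (c) substance use disorder within the past 12 months per DSM-V criteria", followed by "d) a prior psychiatric condition requiring hospitalization". Withdrawal is not mentioned.
- **Target population.** The first paragraph requires that subjects have no alcohol use disorder. The second excludes anyone who has met the criteria in their lifetime.

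The treatment window also varies. The Key Exclusion Criteria use "a desire for alcohol treatment now or received it in the past 6 months", and the other two lettered lists agree on 6 months. The first paragraph of Target population instead requires no treatment in the past year.

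**The concern.** Every participant is given three doses of alcohol aimed at a BAC of 0.10. Potential Study Risks defends that exposure partly on the ground that these moderate drinkers have taken a similar amount before, so the defence depends on who is enrolled. Whether a person with alcohol use disorder may be dosed is a basic safety rule, and the protocol answers it in two ways. The weaker answer appears at phone screening, the step staff carry out to decide who is booked. What is at stake is participant protection and a clear definition of the enrolled population.

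**Working it through.** No arithmetic applies beyond counting. The check sets the texts side by side and follows three hypothetical people through them.

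**Step 1. The rule in each place**

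| Place | Alcohol-disorder exclusion | Treatment window |
|---|---|---|
| Administration of Surveys and/or Process | Use disorder, only with withdrawal | 6 months |
| Target population, first paragraph | Use disorder, no time frame | 1 year |
| Target population, second paragraph | Use disorder, lifetime | none given |
| Key Exclusion Criteria | Use disorder, no time frame | 6 months |
| Procedures, Phone Screening | Dependence, only with withdrawal | 6 months |

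Two of the five places carry the withdrawal condition and three do not. Of the three lettered exclusion lists, two carry it and one, the Key Exclusion Criteria, does not.

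**Step 2. Who falls between the rules**

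- *Current alcohol use disorder, no withdrawal.* Barred by the Key Exclusion Criteria and by both paragraphs of Target population. Passes the alcohol-disorder item in the other two lists.
- *Past alcohol use disorder, none now, no withdrawal.* Barred by the second paragraph of Target population. Unclear under its first paragraph and under the Key Exclusion Criteria, which give no time frame. Passes the item in the other two lists.
- *Treated for alcohol 9 months ago (illustrative).* Outside the population in the first paragraph of Target population, but passes the treatment item in all three lettered lists.

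**Step 3. Would a later step catch the first person?**

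- The Study Visit item names photo ID, a zero breath reading, blood pressure, heart rate and a urine pregnancy test. It also mentions a screening and medical history, and says participants are deemed eligible. It names no check for alcohol use disorder.
- The survey-administration section mentions a "preliminary study visit for participants to consent to the study and complete the eligibility survey", but says of in-person attendance beforehand: "There will be an optional in person study visit". Subject Confidentiality says only that participants may be asked to meet staff first.
- The section on assigning subjects to groups limits randomisation to those who meet eligibility criteria, without saying which list it means.
- The Screening Survey and Eligibility Survey are attachments that are not in the available documents.

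So no later check for the disorder is shown, and none can be ruled out.

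**Step 4. Exclusions missing from the Key Exclusion Criteria**

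Pregnancy is an exclusion in the survey-administration list and in Target population. Nursing and psychotropic medication are exclusions only in Target population. The Key Exclusion Criteria name none of these three. They do cover medication that limits or prevents drinking, which is a different test.

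**The case against.** The strongest reply is that the phone list is a summary. It omits suicidal ideation, yet the same step administers the Columbia scale. It omits pregnancy, yet a urine test precedes dosing. The section on waiver of consent implies that the phone survey collects psychiatric and substance use history, which goes beyond the printed list. The section headed Key Exclusion Criteria is the natural governing text, and Target population agrees with it. Every version excludes the disorder when withdrawal is present. The drinking limits (under 4 days and under 12 drinks a week), prior tolerance of 4 drinks for women or 5 for men, an onsite nurse, and observation until the breath reading falls to about 0.03 all reduce the risk.

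Most of this stands, and it limits the point in four ways. A reader might infer:

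- **that substance use disorder and psychiatric hospitalisation are not screened for**, because the phone list leaves them out. A partial list does not show that; they are unlisted, not shown to be unapplied.
- **that there are four competing definitions**, by counting the statements in the Brief description and Accrual that subjects are without dependence. Those are summary statements. The real conflict is two-way, with or without the withdrawal condition, plus an unsettled time frame.
- **that people with alcohol use disorder will be dosed.** That depends on forms the documents do not show.
- **that the arm comparison is biased.** Eligibility is settled before randomisation, and the same screening applies to both arms.

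The reply does not remove the core. The withdrawal condition is not an omission from a summary. It is a different stated rule, printed in two full lists. A stricter attached form would lower the practical risk but leave the protocol contradicting itself.

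**Conclusion.** The point holds as an inconsistency in a safety criterion that should be fixed. As written, phone screening can clear a person with alcohol use disorder but no withdrawal whom the Key Exclusion Criteria bar, and no later step shown names a check that would catch this. Confidence is high on the wording. It is lower on the practical consequence, which assumes that staff apply the printed list and that the unseen forms do not already apply the broader rule. The number of participants affected, out of at most 30, cannot be estimated from the documents. The treatment window and the exclusions scattered across sections are secondary, and matter mainly because a repair must not lose any of them.

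**What to change.** 1. Delete the withdrawal condition from the Phone Screening item and from Administration of Surveys and/or Process, and use the term alcohol use disorder in both, so that they match the Key Exclusion Criteria.
2. State whether the exclusion is lifetime or current. This is the sponsor's decision; the second paragraph of Target population already says lifetime.
3. Declare the Key Inclusion and Key Exclusion Criteria the governing list, and add pregnancy, nursing and psychotropic medication to it. Making it the sole reference without these additions would leave an alcohol-dosing study with no express pregnancy exclusion in its governing criteria.
4. Set one treatment window, 6 months or 1 year, and use it throughout.
5. Have the phone screener, and a pre-dose check in the Study Visit item, confirm every entry on that list.

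The cost is protocol and form wording, a few more screening questions, and a possibly narrower recruitment pool, which could slow enrolment in a study of up to 30 people planned for 10 weeks.

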#### Timeline: Study activities at Site Visit

Time	Procedures *
00 - 10 minutes	
 
Participant is given a priming dose of alcohol containing vodka in fruit juice designed to raise the BrAC to 0.03-0.04 g/dL based on calculations based on weight and gender
 

10-30 minutes	
 
Participant rinses with alcohol free mouthwash or water
 

30-40 minutes	
 
Measurement of BrAC with BacTrack mobile breathalyzer
 
Control: Blinded to BrAC reading. Intervention: Shown BrAC reading on BacTrack mobile app
 
Self Report of Intoxication Survey
 

40-50 minutes	
 
Second dose of alcohol designed to raise BrAC to 0.07-0.08'
 

50-70 minutes	
 
Participant rinses with alcohol free mouthwash or water
 

70-80 minutes	
 
Measurement of BrAC with BacTrack mobile breathalyzer
 
Control: Blinded to BrAC reading. Intervention: Shown BrAC reading on BacTrack mobile app
 
Self Report of Intoxication Survey
 

80-90 minutes	
 
Participant receives third dose of alcohol containing vodka in fruit juice designed to raise the BrAC to 1.01-1.02 g/dL
 

90-110 minutes	
 
Participant rinses with alcohol free mouthwash or water
 

110-120 minutes	
 
Measurement of BrAC with BacTrack mobile breathalyzer
 
Control: Blinded to BrAC reading. Intervention: Shown BrAC reading on BacTrack mobile app
 
Self Report of Intoxication Survey
 

135 minutes	
 
Measurement of BrAC with BacTrack mobile breathalyzer
 
Control: Blinded to BrAC reading. Intervention: Shown BrAC reading on BacTrack mobile app
 
Self Report of Intoxication Rating Survey:
 

150 minutes	
 
Measurement of BrAC with BacTrack mobile breathalyzer
 
Control: Blinded to BrAC reading. Intervention: Shown BrAC reading on BacTrack mobile app
 
Self Report of Intoxication Rating Survey:
 

175 minutes	
 
Measurement of BrAC with BacTrack mobile breathalyzer
 
Control: Blinded to BrAC reading. Intervention: Shown BrAC reading on BacTrack mobile app
 
Self Report of Intoxication Rating Survey:
 

190 minutes	
 
Measurement of BrAC with BacTrack mobile breathalyzer
 
Control: Blinded to BrAC reading. Intervention: Shown BrAC reading on BacTrack mobile app
 
Self Report of Intoxication Rating Survey:
 

205 minutes until study completion	
 
Measurement of BrAC with BacTrack mobile breathalyzer
 
Control: Blinded to BrAC reading. Intervention: Shown BrAC reading on BacTrack mobile app
 
Self Report of Intoxication Rating Survey:
 
Breathalyzer measurements will be obtained until participant is at .03 or lower
 

Deception: Does your project use deception?

NO

Deception could be considered any direct misinformation presented to the subject or omission of key information pertaining to the design or nature of the project.

NO

Are you conducting research outside of the United States? \*

NO

Analysis Plan: Describe briefly the statistical methods used to analyze the data

Data analysis will be led by [name], Professor of Biostatistics.

Primary outcome:

We will test for differences in perceived fitness to drive according intervention arm and BrAC level accounting for clustering of measurements within participants and time from the first drink using a generalized linear model with a logit link. We will then explore the mediating effects of baseline demographic and psychological variables with inclusion of these variables in the model.

**Secondary outcomes:** We will conduct descriptive analyses exploring the effect modification of baseline demographic and psychological measures on these differences including: age, sex, BMI, past level of alcohol consumption, delay discounting rate, and the Barrat's impulsivity scale.

**Subject Confidentiality:** Confidentiality refers to the researcher's agreement with the participant about how the participant's identifiable private information will be handled, managed, and disseminated. The research proposal should outline strategies to maintain confidentiality of identifiable data, including controls on storage, handling, and sharing of data. When developing strategies for the protection of subjects' confidentiality, consideration will be given as to:

Participants who have seen recruitment material will call a study line in order to sign up for the study. At this pre-screening phone call, the research project manager will briefly go over study procedures. If the participant is interested, they will be complete a brief (less than ten minute) screening over the phone to determine eligibility. Participants may be asked to meet with the study staff prior to scheduling their study visit to determine eligibility. At the study visit, eligible participants will sign written informed consent, and be administered the study protocol; all study documents will be de-identified after all contact has been made. Participant information will be stored in a locked filing cabinet only accessible by the research assistants, PI, and project manager. Personal information will not be stored with study data and will be destroyed after data collection.

**Sensitive Research Information:** Does this research involve collection of sensitive information about the subjects that should be excluded from the electronic medical record? [NOTE: This does not apply to: 1) research information that would not normally be included in the electronic medical record or 2) information that is in the electronic medical record as part of clinical care.]

NO

**Data Disclosure:** Will the data be disclosed to anyone who is not listed under Personnel? If so, identify disclosures.

No. Participant BrAC measurements and survey responses from participants will not be linked to participant identifying information, and data will be available only for study personnel. However, all potential subjects will be informed that the information they provide will be held in confidence to the extent that the law allows, but that the exception to this confidentiality is any disclosure of potential for immediate harm of themselves or others, such as active suicidal or homicidal ideation or child abuse. The participants will be notified prior to participation that if any of these issues are raised, the researchers will take whatever steps are necessary to protect the subject or others, including bringing risk of harm to the attention of the proper authorities. As an emergency physician, [name] is experienced with assessing this type of risk and committing patients or notifying child protective services or law enforcement when necessary.

Protected Health Information/Data Protection: Describe if data to be used or collected involves any protected health information (PHI) and specify which PHI is to be used/collected. Health information is determined to be PHI if it contains any of the following identifiers:

Name

Street address, city, county, precinct, zip code, and equivalent geocodes

All elements of dates (except year) for dates directly related to an individual and all ages over 89

Telephone and fax number

Electronic mail addresses

Social security numbers

Medical record numbers

Health plan ID numbers

Account numbers

Certificate/license numbers

Vehicle identifiers and serial numbers, including license plate numbers

Device identifiers/serial numbers

Web addresses (URLs)

Internet IP addresses

Biometric identifiers, incl. finger and voice prints

Full face photographic images and any comparable images

Any other unique identifying number, characteristic, or code

None

Consent Process: Overview\*Summarize how informed consent will be obtained, including how, when, where, and by whom it will be obtained. Describe any waiting period between informing the prospective participant and obtaining the consent. Describe any steps taken to minimize the possibility of coercion or undue influence. Describe the language used by those obtaining consent. Describe the language understood by the prospective participant or the legally authorized representative.

Participants will respond to recruitment material by calling the study hotline. After calling the study hotline, participants will be screened for eligibility and will schedule a visit. At the study visit, participants will sign written informed consent. Consent will be obtained by explaining the study

objectives, procedures, and potential risks to subjects verbally and in writing at a pre-screening and / or screening visit. Subjects will be given an opportunity to ask questions and will be provided with complete and accurate answers to any questions they may have. Written documentation of this process will be obtained using the IRB-approved consent form. Subjects are given a signed copy of the consent form for his or her reference.

Children and adolescents

not applicable.

Adult subjects not competent to give consent

Participants will be excluded from the study if they are not competent to consent to the study.

Does your research request both a waiver of HIPAA authorization for collection of patient information and involve providing Protected Health Information ("PHI") that is classified as a "limited data set" (city/town/state/zip code, dates except year, ages less than 90 or aggregate report for over 90) to a recipient outside of the University of Pennsylvania covered entity? **NO**

Waiver or Alteration of Informed Consent: Are you requesting a waiver of, or alteration to, the informed consent process? Please choose one of the following and provide justification where appropriate: **YES**

Minimal Risk\*

The research involves no more than minimal risk to the subject

This research in general involves minimal risks to the participants because the benefits outweigh the risks in this study. Specifically the waiver of consent only applies to administration of the screening survey, and completing this survey involves minimal risk to participants, such as there is some risk that confidential information provided regarding psychiatric and substance use history will be inadvertently disclosed without the subjects' permission. Methods outlined elsewhere in this protocol will be in place to protect participant information to minimize this risk. Also the benefits for allowing participants to take screening over the phone and not having to come in for two study visits outweighs this risk.

Impact on Subject Rights and Welfare\*

The waiver or alteration will not adversely impact the rights and welfare of the subjects.

We will require a waiver of consent written consent in order to administer the screening survey over the phone because it is not feasible for each participant to be required to come in, in order to answer questions in the screening survey. Before the screening survey is administered, participants will be prompted to provide verbal consent over the phone, using the verbal consent script that is attached to this protocol. Once a participant is screened, using the screener, and has set up a study session, participants will signed written informed consent at the beginning of their study visit prior to any other activities being completed.

